2.3 Rationale

In the last half century, there have been few advances in the pharmacologic management of acute anxiety. As one example, a panic attack in 2019 is managed as it was in 1969: with a class of medications called benzodiazepines. While effective, benzodiazepines carry hefty risk profiles that include, acutely, cognitive slowing, even frank confusion, hypersomnia, perceptual disturbances, anterograde amnesia, accidental overdose, ataxia and hypotension, leading to falls and other injuries. Long-term benzodiazepine use may result in dependence, abuse, and a withdrawal reaction upon discontinuation.

The lack of pharmacologic innovation in the management of acute anxiety is particularly concerning to oncology, where anxiety is ubiquitous. According to one study, 42% of cancer patients manifest clinical anxiety after cancer diagnosis⁹. Cancer-related concerns are myriad and include health and existential anxieties (for instance, after receipt of alarming test results), psychosocial worries (for instance, around the impact of cancer on occupation and family), and fears regarding procedures (for instance, chemotherapy infusions, surgeries and scans to assess tumor burden). Of note, the anxiety tied to radiographic procedures to assess tumor burden peaks prior to the actual scan (rather than during or after).^{10,11} While management strategies include relaxation techniques, psychological treatments such as counseling, and antidepressants, the mainstay of treatment for moderate to severe acute cancer-related anxiety remains benzodiazepines. Although rates of benzodiazepine use among cancer patients have not been published in the last three decades, previously published rates range from 16-25%¹². We suspect that current rates are higher, first because prescription benzodiazepine use is on the rise in the United States¹³ and, second, because the National Comprehensive Cancer Network now identifies benzodiazepines among the chief management strategies for anticipatory nausea and vomiting with chemotherapy¹⁴. Of note, the DFCI website prominently encourages use of benzodiazepines prior to radiographic imaging¹⁵.

Common, however, is not necessarily good. The risks attending benzodiazepine use can be magnified in cancer patients who are more likely to be frail and elderly. In addition, benzodiazepine use prior to an oncology appointment in which important medical information is to be transmitted may impair patient comprehension and decision-making ability. In the general public and, especially, in cancer populations, safer, effective alternatives to benzodiazepines are warranted.

Cannabidiol, a non-intoxicating, non-addictive cannabis ingredient, may confer similar benefits to benzodiazepines with fewer risks^{7,16}. Preclinical and clinical studies suggest that CBD possesses anxiolytic, antipsychotic, sedative, anticonvulsive, antiemetic, anti-inflammatory,

analgesic, and antitumor effects³⁻⁶. For instance, using a cross-over model, Crippa et. al. demonstrated through subjective report, physiological parameter testing, and functional neuroimaging that CBD significantly ameliorates reactive anxiety in healthy normals (2004; N=10; anxiety provoking stimulus: MRI), those with generalized social anxiety disorder (2011; n=10), and those with social phobia;⁷ n=30). Although the biochemical mechanism of cannabidiol has not yet been fully elucidated, 5HT_{1A} receptors in limbic and paralimbic areas are postulated to mediate its anxiolytic effects⁷.

In all human studies (including these), CBD was well-tolerated and, despite existing in the same plant as tetrahydrocannabinol, seems to have different and sometimes opposing effects to it^{3,5}. Administered acutely across a wide variety of oral (15 mg to 600 mg), intravenous (5 to 30 mg) and inhaled (0.15 mg/kg) doses, CBD produced no notable emotional, cognitive, psychomotor or vital sign side-effects⁷. Similarly, neither chronic administration up to 300 mg orally for 4.5 months (n=15) nor, in a case report, 1500 mg/day for four weeks produced notable side-effects^{17,18}. In the case of the former, neurological and physical examinations, blood and urine analyses, electrocardiograms and electroencephalograms were performed at regular intervals. In fact, the United States Food and Drug Administration (FDA) recently approved pharmaceutical-grade CBD manufactured by GW Pharmaceuticals under the trade name Epidiolex for management of forms of pediatric epilepsy. This approval, coupled with the United States Drug Enforcement Agency (DEA) rescheduling of it has opened the door more widely to clinical trials of CBD in oncology.

In this study we hope to test the preliminary efficacy of a single dose of oral cannabidiol (CBD) in reducing anticipatory anxiety in patients with advanced breast cancer. The inciting stressor in the study is anticipation of radiographic assessment of tumor burden. Research indicates that, in cancer patients undergoing positron emission tomography/computed tomography (PET/CT) scans, prescan anxiety is considerably elevated above post-procedure levels¹⁹. This finding is likely due to concerns about undergoing the procedure itself coupled with concerns about the prognostic results it may herald¹⁹. Of note, no differences in anxiety amplitude were noted between patients who were naïve to the procedure and those who had undergone PET/CT previously¹⁹.

2.4 Correlative Studies Background

N/A

3. PARTICIPANT SELECTION

3.1 Eligibility Criteria

3.1.1 Diagnosis of Stage IV or metastatic breast cancer

3.1.2 Age \geq 18 years.

3.1.3 Karnofsky \geq 60%.

3.1.4 Participants must have adequate organ and marrow function at baseline as defined below:

- total bilirubin \leq 2 times institutional upper limit of normal (ULN)
- AST(SGOT)/ALT(SGPT) \leq 3 \times institutional ULN

3.1.5 Baseline at least mild anxiety as measured by GAD-7 \geq 5

3.1.6 Experience of at least mild anxiety typically tied to anticipation of oncologic scans (as measured by a prescreen survey item)

3.1.7 Computed tomography or positron emission tomography (PET) to assess tumor burden scheduled for within 48 hours of study drug administration

3.1.8 No cannabis, delta-9-tetrahydrocannabinol or cannabidiol use within 24-hours of study drug administration.

3.1.9 No benzodiazepine consumption within 8 hours of study drug administration (e.g., nighttime benzodiazepine use permissible)

3.1.10 No driving for 12 hours following study drug administration.

3.1.11 English proficiency

3.1.12 The effects of cannabidiol (Epidiolex) on the developing human fetus are unknown. For this reason and because cannabis is known to be teratogenic, women of child-bearing potential must not be pregnant when entering the study. The study team will encourage women of child-bearing age to use adequate contraception (hormonal or barrier method of birth control; abstinence) prior to study entry and for the duration of study participation. Should a woman become pregnant or suspect she is pregnant while she is participating in this study, she should inform her treating physician immediately. Women must agree to use adequate contraception prior to the study, for the duration of study participation, and for 1 week after cannabidiol (Epidiolex) consumption. Women either age \geq 54 years, or documented to be in menopause, or status post hysterectomy will not be required to obtain bHCG.

3.1.13 Ability to understand and the willingness to sign a written informed consent document.

3.2 Exclusion Criteria

3.2.1 History of allergic reactions attributed to compounds of similar chemical or biologic composition to cannabidiol (Epidiolex) or placebo (which contains sesame, corn and gluten)

3.2.2 Current clobazam or valproic acid use

- 3.2.3 Current uncontrolled illness, for instance sepsis, symptomatic congestive heart failure, unstable angina pectoris, cardiac arrhythmia
- 3.2.4 Current use of antiretroviral therapy
- 3.2.5 Participants with psychiatric illness or social situations that would limit compliance with study requirements
- 3.2.6 Current hepatocellular carcinoma or documented history of difficult to control diabetes
- 3.2.7 Active participation in a clinical drug trial

3.3 Inclusion of Women and Minorities

Women of all races and ethnic groups are eligible for this trial. Men will be excluded.

4 REGISTRATION AND RANDOMIZATION PROCEDURES

4.1 General Guidelines for DF/HCC Institutions

Institutions will register eligible participants in the Clinical Trials Management System (CTMS) OnCore. Registrations must occur prior to the initiation of any protocol-specific therapy or intervention. Any participant not registered to the protocol before protocol-specific therapy or intervention begins will be considered ineligible and registration will be denied.

An investigator will confirm eligibility criteria and a member of the study team will complete the protocol-specific eligibility checklist. The randomization in this trial will be stratified on baseline anxiety level: Mild to moderate (5-14) versus Severe (15-21).

Following registration, participants may begin protocol-specific therapy and/or intervention. Issues that would cause treatment delays should be discussed with the Overall Principal Investigator (PI). If the subject does not receive protocol therapy following registration, the subject must be taken off study in the CTMS (OnCore) with an appropriate date and reason entered.

4.2 Registration Process for DF/HCC Institutions

Applicable DF/HCC policy (REGIST-101) must be followed and adobe e-sign for consent

4.3 General Guidelines for Other Investigative Sites

Not Applicable

4.4 Registration Process for Other Investigative Sites

Not Applicable

5. TREATMENT PLAN

5.1. Treatment Regimen

5.1.1 Enrolling sites and study entry

A sample of 200 participants who are scheduled undergo computed tomography (CT) scan or positron emission tomography (PET) to assess tumor burden will be recruited to a randomized control study in which they will receive a single dose of cannabidiol (Epidiolex) versus placebo. Accrued patients will continue on the study and will be randomized only if they meet the eligibility criteria at baseline (described below). Consenting and accrual will stop early if 50 patients meeting eligibility (final sample needed for the study) are randomized and enrolled on to the study.

A study team member will screen potential participants using the daily appointment logs of the DFCI Breast Oncology Center and the DFCI Department of Imaging. The study will also accept referrals from the Breast Oncology Program. We will also obtain a list of participants on 09-204, to aid in our recruitment activity. We will present the study at patient forums; post study flyers in waiting rooms including virtual screens; post the study to DFCI websites (e.g., YAP@DFCI) distribute flyers at local cannabis dispensaries and cannabis certifiers to inform participants about the study (Appendix A: Study Letter & Recruitment Flyer). We will obtain a HIPAA waiver to enable medical record screening of potential participants. Once potential participants are identified, we will notify the primary oncologist of their patient's eligibility via pager, email or in person. Providers need only contact the study team if they do not wish their patient to participate in the study.

Study staff will approach the patient in clinic or schedule a virtual visit with the potential participants to introduce the study (Appendix A: Study Letter & Recruitment Flyer). They will assess eligibility and give potential participants time to ask questions and consider study participation. A licensed physician will answer questions and obtain consent from eligible participants (either in-person or remotely using Adobe eSign).

Once inclusion criteria have been met and exclusions ruled out, study staff will follow the registering processes described in Section 4.0. Participants will be randomized in a 2:1 fashion to CBD or placebo using permuted blocks within strata and a double-blind procedure will be followed. Randomization will be completed by the Office of Data Quality (ODQ). The eligibility checklist(s) and all pages of the consent form(s) will be faxed to the ODQ at [contact]. The ODQ will (a) review the eligibility checklist, (b) register the participant on the protocol, and (c) randomize the participant.

All survey assessments will be completed either in-person or remotely (either through RedCap, phone, text messaging or by mail).

Baseline: Following consent, if necessary (i.e., no such values exist in the chart within the last 6 weeks +/- 7 days), the patient will complete laboratory assessments, as well as a series of

surveys. If during the course of these assessments, the patient is determined to not meet eligibility criteria, they will be taken off study. Once the study team receives baseline assessment, the participant will be scheduled for Study Timepoint 1, which will take place within 48 hours of the anticipated CT scan or positron emission tomography (PET) to assess tumor burden. Study staff will follow up via phone, email, and/or mail to remind the study participant of the scheduled study visit.

Treatment Day:

The Treatment Day will take place within 48 hours of anticipated CT scan or positron emission tomography (PET) to assess tumor burden (based on the study participant's radiology appointment schedule). The study team will contact the participant approximately 24 hours before Timepoint 1 to ensure that the participant abstains from cannabis and benzodiazepine uses. Timepoint 1 (Pre-drug Administration Visit) will be completed prior to study drug administration. Observation for the drug administration is noted in section 5.3. Timepoint 2 (Post-drug Administration) will take place approximately 3(+/-1) hours following study drug administration. In total the treatment day inclusive of timepoint 1 and timepoint 2 will be approximately 8 hours(+/-1).

Timepoint 1 (Pre-drug Administration): Regardless of randomization arm, all participants will complete a set of questionnaires. The study team will review questionnaire responses assessing cannabis and benzodiazepine uses (e.g. section 3.1.8 & 3.1.9 of the eligibility criteria). If a participant indicates they have consumed either within the prohibited timeframe, the study team will attempt to delay study drug administration in order to meet eligibility criteria. (Section 5 offers full details on consuming study drug). However, if the study drug administration cannot be delayed, the Treatment Day will be rescheduled to coincide with the next scheduled CT scan or positron emission tomography (PET). See section 8.1.11. for unused study drug destruction.

Timepoint 2 (Post-drug Administration): All participants will complete a set of questionnaires.

Timepoint 3: Study staff will phone the participant within a week +/- 7 days of study drug consumption to conduct a brief, semi-structured audio-recorded interview.

At study completion participants will receive a \$50 gift card. They will also receive up to \$50 for qualifying study-related travel costs and/or expenses. After all study procedures are completed, the research team will contact participants to inform of which arm they were assigned after unblinding and share any publications that come from this study.

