5.1.3 Instruments measuring study outcomes:

Demographic questionnaire (Baseline):

Variables of interest will be obtained via self-report and include: age, ethnicity, race, marital status, education, and occupational status.

Cannabis History Questionnaire (Baseline):

Cannabis use history will be obtained via self-report.

Generalized Anxiety Disorder- 7 (GAD-7) (Baseline, Timepoint 1): The widely used and validated GAD-7 measures anxiety severity on a 4-point Likert-type scale from not at all to

nearly every day. The presence of baseline anxiety, as measure by a GAD-7 score >4 , is necessary for inclusion in this study.

Patient Health Questionnaire (PHQ-9) (Baseline, Timepoint 1): The widely used and validated PHQ-9 is a 9-item depression severity measure, with scores ranging from 0 to 27. Patients are asked to rate how they felt over the past two weeks using a 4-point Likert scale. Given that anxiety and depression are closely intertwined, this measure will help us to demonstrate that the active drug and placebo arms manifest similar levels of dysphoric distress. This measure will also help in screening to rule out “uncontrolled mental illness.”

VAMS (Timepoint 1, and Timepoint 2): The Visual Analog Mood Scale (VAMS) a validated in-the-moment measure of eight specific mood states: Afraid, Confused, Sad, Angry, Energetic, Tired, Happy, and Tense. Each scale consists of a 100 mm vertical line connecting a neutral face and a face displaying a particular mood state (with an accompanying descriptor). Subjects are asked to mark their mood along this continuum. The measure is scored using a metric ruler and the “Afraid” subscale will serve as our primary endpoint. Other subscales will serve as exploratory endpoints.

EORTC-QLQc30-nausea (Timepoint 1, and Timepoint 2): The EORTC-QLQc30-nausea is a widely used and validated measure of symptom burden. It consists of 30-items, the first 28 of which employ a four-point scale (the final two are measured along a seven-point scale). Single item measures range in score from 0 to 100, with higher scores representing lower symptom burden. For the purposes of this study we will administer two items from the EORTC-QLQc30 on nausea and vomiting to assess a secondary endpoint.

Numeric Pain Rating Scale (Baseline, Timepoint 1, Timepoint 2): This widely used in-the-moment pain intensity scale is scored from 0 to 10 (with 10 representing “worst possible” pain). The NPRS will again help us to assess secondary endpoints.

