8.1.8. Administration

Disposable 10mL oral syringe will be used to administer cannabidiol (Epidiolex) PO at the conclusion of Timepoint 1.

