11. STATISTICAL CONSIDERATIONS

This is a phase II, randomized, placebo-controlled study to assess the preliminary efficacy of offering a single dose of CBD versus placebo in reduction of anxiety in patients with advanced (stage IV) solid tumor anticipating CT to assess tumor burden. Eligible patients must have measurable anxiety-- at least “mild” anxiety as measured by the GAD-- at the pre-screen visit.

Anxiety level at each of the time points (pre-screening visit, pre-dose, and 3[+/-1] hour post dose) will be plotted for each study group. The paired change (pre-dose to post-dose) in anxiety will be estimated along with a 95% confidence interval for each study group. The change in anxiety will be compared by study group with a Wilcoxon rank sum test. The side-effect profile, as measured by the PRO-CTCAE will be tabled according to side effect. Patient reported experience with CBD and the acceptability will be summarized with descriptive statistics and qualitative methodology as appropriate

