11.1. Study Design/Endpoints

Primary Endpoint

Change in anxiety will be assessed by the Visual Analog Mood Scale (VAMs) anxiety subscale, ascertained on the day of the drug administration pre-dose (T1) and 3(+/- 1) hour after drug administration (T2). The change in anxiety score will be calculated for each patient and a Wilcoxon rank sum test will be used to assess whether the change score is different among patients randomized to CBD as compared to placebo.

Secondary and Exploratory Endpoints

Secondary and exploratory objectives include a description of the side-effect profile of CBD in oncology patients, patient reported experience and acceptability of CBD, and the estimation of the change in state anxiety as well as other VAMs subscales (Afraid, Confused, Sad, Angry, Energetic, Tired, Happy, and Tense). Secondary endpoint analyses will be considered exploratory (no alpha adjustment given the relatively small sample size) and will provide context for interpretation of the primary endpoint.

Randomization

Patients will be randomized 2:1 to CBD or placebo using permuted blocks within strata (one single stratification variable, baseline anxiety with 2 levels, will be used) and a double-blind procedure will be followed. Randomization will be completed by the Office of Data Quality (ODQ). ODQ will send the randomization assignment to the DFCI Research Pharmacy and the pharmacy will dispense the medication. The justification for the 2:1 randomization is to better assess side-effects and to allow for more qualitative data at the completion of the study.

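### A same-day dose delay after recent benzodiazepine or cannabis use does not trigger a repeat of the Timepoint 1 VAMS, so the primary baseline can be taken inside the prohibited window

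*Combined protocol and SAP*

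**What the plan says.** - **Delay rule (5.1.1, Timepoint 1).** All participants complete the questionnaires, and the team then reviews the answers on cannabis and benzodiazepine use. If use falls in the prohibited period, "the study team will attempt to delay study drug administration in order to meet eligibility criteria". If no delay is possible, the Treatment Day moves to the next scheduled scan.
- **Washout (3.1.8, 3.1.9).** The benzodiazepine rule reads "No benzodiazepine consumption within 8 hours of study drug administration", with night-time use given as permissible. The cannabis rule is 24 hours. Both run back from the dose, not from the VAMS.
- **Instrument (5.1.3, Section 9).** The VAMS is described as "a validated in-the-moment measure of eight specific mood states" and is scheduled once at T1 and once at T2.
- **Primary endpoint (11.1).** The change from T1, taken before the dose on the day of drug administration, to T2, taken 3 (±1) hours after the dose. Section 11 adds: "The paired change (pre-dose to post-dose) in anxiety will be estimated along with a 95% confidence interval for each study group".
- **Timing (5.1.1).** The treatment day, including T1 and T2, lasts about 8 (±1) hours.
- **Link between dose and T1.** Section 8.1.8 gives cannabidiol "at the conclusion of Timepoint 1". The regimen table in 5.1.2 places both agents at Timepoint 1. The Section 9 footnote says only that the drug follows the pre-assessments.
- **Section 6.** Dosing delays are said to be neither allowed nor applicable, which conflicts with 5.1.1.

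**The concern.** The answers that trigger a delay belong to the same T1 set as the primary baseline, so by the time a delay is ordered the baseline has normally been recorded. For a benzodiazepine delay, that baseline lies by definition less than 8 hours after the drug. The dose then waits for the 8 hours to pass, and T2 comes 3 hours later, at least 8 + 3 = 11 hours after the benzodiazepine (10 at the lower tolerance).

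The washout rule thus protects the dose and T2 but not the baseline. On a momentary scale, a baseline lowered by a benzodiazepine makes the later reduction in fear look smaller, and hours of waiting for a scan can move the score as well. A baseline recorded this way cannot be recovered afterwards.

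**Working it through.** **1. The plan's own figure.** Section 11.2 gives 45 evaluable patients (30 v 15) for 80% power with a two-sided 0.05 Wilcoxon test, difference 20, SD 20. Noether's formula with P = Φ(1/√2) = 0.760 gives N = (1.960 + 0.842)² / [12 × (1/3) × (2/3) × (0.760 − 0.5)²] = 43.5, so 44. At the lower-bound Wilcoxon efficiency of 0.864 the noncentral t gives 45. With normal data, power at 30 v 15 is about 0.85. Enrolment is 45/0.9 = 50. The plan's figures reproduce.

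**2. How long a same-day delay can be.** Treatment-day length minus dose-to-T2 time, ignoring questionnaire time:
- nominal: 8 − 3 = 5 h
- at the tolerance limits: 9 − 2 = 7 h

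The limit is soft, because the text does not say whether the 8-hour day still applies once a dose is delayed.

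**3. Who can be delayed on the same day.** With last use t hours before T1, the delay needed is 8 − t (benzodiazepine) or 24 − t (cannabis). A 5 h limit covers benzodiazepine use about 3–8 h before T1, and cannabis use only about 19–24 h before T1. Illustration with assumed clock times: a benzodiazepine at 02:00 and T1 at 08:00 needs a 2 h delay; a 22:00 bedtime dose needs none.

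**4. Effect on the primary test.** The documents give neither the share delayed (p) nor the baseline shift (d); both are assumed. Simulation: normal change scores, 30 v 15, SD 20, difference 20, two-sided Wilcoxon at 0.05 (normal approximation with continuity correction), 100,000 trials per case. Each patient in either arm is delayed with probability p, and the recorded reduction is then d points too small. With none delayed, power is 0.851.

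| p | d = 10 | d = 20 | d = 30 |
|---|---|---|---|
| 5% | 0.844 | 0.835 | 0.820 |
| 10% | 0.840 | 0.820 | 0.790 |
| 20% | 0.835 | 0.796 | 0.737 |

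Six of the nine cases stay at or above 80%. With a true difference of zero (60,000 trials per case), type I error is 0.047–0.050. The central case raises the SD from 20 to √(400 + 0.10 × 0.90 × 20²) = 20.9.

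**5. Anchoring p.** The nearest figure is benzodiazepine use of 16–25% in cancer patients (Section 2.3). If a quarter to a half of users dosed inside the 8 h window (assumed), p = 0.16 × 0.25 = 4% to 0.25 × 0.5 = 12.5%, and power is 0.85 to 0.78. Only about 5 of those 8 hours lead to a same-day delay. With uniform timing (assumed), p = 4% × 5/8 = 2.5% to 12.5% × 5/8 = 7.8%, and power is 0.85 to 0.80.

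**6. Effect on the within-arm change.** Shift = p × d, in both arms: 0.05 × 10 = 0.5 to 0.20 × 30 = 6 points; centrally 0.10 × 20 = 2 points. The 95% CI half-widths are 2.045 × 20/√30 = 7.5 (cannabidiol) and 2.145 × 20/√15 = 11.1 (placebo).

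**The case against.** The strongest reply is that the plan ties the dose to T1. Section 8.1.8 and the regimen table can be read to mean that T1 moves with a delayed dose. That reading is reasonable, but 5.1.1 delays only the drug, after the questionnaires are done, and nothing orders a repeat. Section 8.1.8 covers cannabidiol only; the matching placebo text in 8.2.8 gives no timing.

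It can also be said that few participants will be affected. Staff contact each of them about 24 hours before T1 to secure abstention, and they reschedule where a delay is not feasible. The benzodiazepine rates in Section 2.3 are at least three decades old and describe any use, not use hours before a visit. The worst case above needs one patient in five delayed with a 30-point shift in each, and Section 11.2 treats 30T as a clinically meaningful change. All of this stands, and it is why the point is minor.

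Three stronger readings are tempting, and the documents do not support them:
- *The T1-to-dose interval is unlimited.* No limit is stated outright, but the treatment-day length and T2 timing imply about 5 h, at most 7 h.
- *The treatment comparison is biased.* The use review comes before a blinded dose, so a delay cannot depend on the arm. The expected shift is the same in both arms, and type I error holds.
- *A rescheduled Treatment Day leaves it unclear which T1 counts.* Section 11.1 places T1 on the day of drug administration, so a rescheduled day has its own T1.

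**Conclusion.** The gap is real but narrow. As written, a participant delayed on the same day can contribute a primary baseline taken inside the prohibited window and up to about 5 h (at most 7 h) before the dose. The consequence is extra noise in the change score and a possible shift in each arm's paired change.

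The central illustration is a loss of about 3 percentage points of power (85% to 82%) and a 2-point understatement of the within-arm change, well inside the confidence half-widths. It rests on an assumed 10% delayed, an assumed 20-point lowering of T1, normal change scores and SD 20. The true frequency and shift are unknown, and the effect is probably small. Even so, closing the gap costs almost nothing. Minor priority.

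**What to change.** Add to Section 5.1.1, Timepoint 1:

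> If study drug administration is delayed after the Timepoint 1 questionnaires, the VAMS, NPRS and nausea items are repeated immediately before ingestion, and the repeat is used as Timepoint 1 in the analysis.

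In Section 6, add *except as described in 5.1.1* to the statement that dosing delays are not allowed, so that the two sections agree.

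Cost: two short protocol edits and a few minutes of repeat questionnaires for delayed participants only, using the remote survey routes that 5.1.1 already allows. Sample size, statistical test and visit schedule are unchanged.
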